4.2 Rationale for the Proposed Study

The aim of this 12-week randomized multicenter double-blind parallel group placebo-controlled dose finding study is to assess the efficacy and safety of three different doses of LC350189 in subjects with hyperuricemia and a diagnosis of gout. Four groups of 38 subjects will be included in the study, including three groups treated with a range of doses of LC350189 and one group treated with placebo.

LC350189 has the potential to address unmet clinical needs for safety and efficacy in subjects with hyperuricemia and a diagnosis of gout. In the first-in-human clinical trial, LC350189 showed good efficacy for lowering SUA and was well tolerated up to 800 mg/day after multiple dosing in healthy subjects. LC350189 has a favorable safety profile in nonclinical studies to support long-term clinical use. Therefore, it is appropriate to investigate several doses of the investigational product in the intended potential target population.

4.3 Summary of Pre-Clinical /Clinical Studies

LC350189 is a novel, non-purine selective inhibitor of XO, with potent *in vitro* and *in vivo* pharmacological activity. In preliminary evaluations of the pharmacological effects of this compound, an *in vitro* enzyme activity assay showed the half maximal inhibitory concentration (IC₅₀) of LC350189 was 0.003 μ M in bovine milk, which is similar to that of febuxostat, and 0.073 μ M in rat plasma. *In vivo* efficacy studies showed the dose and concentration of LC350189 causing 50% of maximum effect (ED₅₀ and EC₅₀) were 10 mg/kg and 0.39 μ g/ml, respectively. Monitoring of plasma orotic acid and orotidine levels demonstrated that LC350189 has good *in vivo* selectivity for pyrimidine synthesis.

In vitro metabolic stability of LC350189 was evaluated in rat, dog, and human liver microsomes for phase I and phase II metabolism. The results showed that LC350189 was metabolically stable in the microsomes of all species. The majority of metabolites were N-deisopropylated LC350189 (M1) and glucuronide conjugates of LC350189 and M1. Prediction of the *in vivo* interaction potential of LC350189 with other drugs showed the inhibitory effect of LC350189 on various cytochrome P450 (CYP) isozyme activities was negligible up to a concentration of 100 μ M.

In studies to evaluate systemic toxicity in rats, the no observed adverse effect levels (NOAELs) were determined to be 12.5 mg/kg in males (2-week repeated dose toxicity study) and 50 mg/kg in females (4-week repeated dose toxicity study) based on nephropathy; kidney lesions are a known rodent-specific effect (Horiuchi et al 1999). NOAEL (12.5 mg/kg) in rats was used to calculate the maximum recommended starting dose (MRSD) for the first-in-human study.

In repeated toxicity studies in dogs, there were no significant toxic effects, except soft stool, diarrhea, and mucous stool observed in the high dose group. These clinical signs were not accompanied by changes to hematology parameters or histological findings in the digestive system, and were not evident during the recovery period. LC350189 showed no specific safety concerns in genotoxicity studies.

In the first-in-human clinical trial (LG-GDCL001), 129 healthy volunteers were enrolled and exposed to placebo, active comparator (febuxostat 80 mg), or a range of doses of LC350189. In the single ascending dose (SAD) study, subjects were administered placebo or LC350189 10 to 600

mg. In the multiple ascending dose (MAD, once daily doses for 7-days) study, subjects were administered placebo, febuxostat 80 mg, or LC350189 100 to 800 mg. There were no deaths, serious adverse events (SAEs), severe adverse events (AEs), or discontinuations due to AEs, and no clinically significant AEs. Specifically, in the SAD study, among subjects administered LC350189 10 mg (n=6), one subject experienced back pain; among subjects administered LC350189 25 mg (n=6), one subject each experienced nasal congestion or sneezing; among subjects administered LC350189 100 mg (n=8), one subject each experienced flushing or headache; and among subjects administered LC350189 200 mg (n=8), one subject each experienced diarrhea, feeling hot, headache, nasal congestion, rhinorrhea, or throat irritation. In the MAD study, among subjects administered LC350189 100 mg (n=8), one subject experienced hematochezia; and among subjects administered LC350189 600 mg (n=8), one subject each experienced diarrhea, flatulence, lip ulceration, or nausea.

Systemic exposure to LC350189 increased with increasing dose in both the SAD and MAD studies, with no significant differences in pharmacokinetic (PK) properties between studies. The range of time to reach maximum plasma concentration (t_{max}) of LC350189 was 1.0 to 6.0 hours after dosing in the SAD study and 1.0 to 5.0 hours in the MAD study, and elimination half-lives were 5.1 to 15.0 hours and 8.6 to 13.8 hours in the SAD and MAD studies, respectively. In the MAD study, steady state was reached after approximately 2 to 3 days. To evaluate the effect of a high-fat diet on the PK profile of LC350189, the PK with a high-fat diet was compared in the 200 mg dose level group. A high fat diet decreased maximum plasma drug concentration (C_{max}) to 62% of the fasting C_{max} , but no significant change in area under the curve (AUC) was observed after food intake. The sUA 24-hour mean serum concentration ($C_{mean,24}$) on Day 1 decreased by 8.7 to 31.7% from baseline in the SAD study. In the MAD study, the decrease in sUA reached steady state on Day 5 in the 100 mg, 200 mg and febuxostat groups, and on Day 6 in other dosage groups, and the percentage decreases in the sUA $C_{mean,24}$ ranged from 53.5 to 91.2%, while that of febuxostat 80 mg was 58.8% on Day 7. The percentage changes in sUA increased with higher doses, and the changes in all dose groups except for 100 mg were statistically different from that of the febuxostat group.

Additional preclinical/clinical information can be found in the Investigator's Brochure.

4.4 Rationale for Treatment and Dose

For this study, the proposed doses of LC350189 are 50, 100, and 200 mg. These doses were chosen based on the first-in-human clinical trial, which showed that LC350189 10 to 600 mg administered in the SAD study and LC350189 100 to 800 mg administered in the MAD study provided robust sUA lowering in healthy volunteers with no significant safety concerns even at 800mg in the MAD study.

The expected therapeutic dose of LC350189 is between 100 and 200 mg to achieve the treatment target based on modeling and simulation of dose using phase I study data. Therefore, LC350189 50 mg was chosen as the minimal dose and LC350189 200 mg as the maximal dose to explore the appropriate dose range based on safety margins from the NOAEL in rat 13-week repeated dose toxicity and phase I study.

Investigational product will be orally self-administered daily by subjects with water and without regard to food. Regardless of subjects' status on ULT at screening, all subjects will be on gout flare prophylaxis for 3 to 5 weeks (between Days -30 and -23 to -1) prior to receiving study treatment and throughout the study.

A treatment period of 12 weeks and a washout/prophylaxis period of 14-26 days were chosen as these represent the timeframe used in Phase II studies investigating the effect of ULTs on sUA and flare incidence in patients with gout ([Gunawardhana et al 2018](#); [Neogi et al 2015](#); [Poiley et al 2016](#)).

5.0 STUDY OBJECTIVES

5.1 Primary Objective

- To assess the efficacy of LC350189 in terms of sUA level <5 mg/dL at Week 12 (Day 84) to find therapeutic dose of LC350189.

5.2 Secondary Objectives

- To assess the efficacy of LC350189 in terms of sUA levels.
- To investigate the PK and pharmacodynamic (PD) characteristics of LC350189 in subjects with hyperuricemia and a diagnosis of gout.
- To assess antiflare activity in subjects with hyperuricemia and a diagnosis of gout.

5.3 Exploratory Objectives

- To explore the metabolic and anti-inflammatory effects of LC350189.

5.4 Safety Objectives

- To assess the safety and tolerability of LC350189.

For a list of the study endpoints please refer to [Table 12-1](#).

6.0 STUDY DESIGN AND DESCRIPTION

6.1 Study Design

This randomized, double-blind, parallel group, placebo-controlled dose finding study will assess the efficacy in terms of sUA lowering (primary endpoint, <5 mg/dL; secondary endpoint, <6 mg/dL) and the safety and tolerability of LC350189. The study will be conducted at multiple sites in the U.S. in up to 152 subjects. If a subject withdraws from the study, the subject will not be replaced.

Subjects will be randomized 1:1:1:1 (n=38 per group) to the test groups: LC350189 50 mg, LC350189 100 mg, or LC350189 200 mg, or the placebo. Each subject will undergo a screening visit 33 to 26 days prior to the first day of the treatment period (Visit 1); a visit 30 to 23 days prior to the first day of the treatment period to enter a washout period and/or initiate prophylaxis (Visit 2); a visit 9 to 4 day(s) prior to the first day of the treatment period to obtain a blood sample to assess eligibility for randomization based on the inclusion criterion of sUA ≥ 8.0 mg/dL to ≤ 12.0 mg/dL (Visit 3); a treatment period that will include five visits on Day 1, 14, 28, 56, and 84 (Visits 4 to 8); and a follow-up on-site visit approximately 2 weeks (Day 98) after completion of the dosing period (Visit 9). The duration of the study will be up to 19 weeks for each subject.

Eligible subjects receiving ULT will discontinue their ULT and enter a wash-out period starting at Visit 2 prior to receiving study treatment. All subjects will receive gout flare prophylaxis with colchicine 0.6 mg (QD) starting at Visit 2 (between Day -30 to -23) through the end of the treatment period.

During the treatment period, subjects will orally self-administer LC350189 or its placebo for 12 weeks starting on Day 1. To maintain consistency, patients will be instructed to take the investigational product at the same time daily, and to withhold the investigational product until after pre-dose laboratory sampling on the days of scheduled visits (Days 14, 28, 56, and 84). At each visit during the treatment period, blood will be sampled for primary, secondary and exploratory endpoint evaluations, and safety assessments will be performed ([Table 12-1](#)). On Day 1 (Visit 4) PK/PD analysis will be conducted pre-dose and 4 hours post-dose for sparse data. For dense data, additional 2, 8 hours and 12 hours post-dose in subjects, who sign written informed consent for dense PK/PD sampling, will be collected on Day 1. On Day 14 and 28 (Visit 5 and 6), PK/PD analysis will be conducted pre-dose for both sparse and dense data. On Days 56 (Visit 7), blood will be sample at pre-dose and 4 hours post-dose for sparse data; and additional 8 hours post-dose for dense data. On Day 84 (Visit 8), pre-dose blood will be sampled at a single time point for PK trough and PD analyses for both sparse and dense data.

Subjects will record the incidence of gout flares using electronic patient diaries (eDiary) from start of prophylaxis (Visit 2) through to end of treatment (Visit 8).

Subjects enrolled to the study before the implementation of the Protocol version 5.0

[figure not shown]
Upon implementation of the Protocol version 5.0, enrollment to the active control group (febuxostat) will be stopped and subjects will be randomized to one of four groups (LC350189 50 mg, LC350189 100 mg, LC350189 200 mg, or placebo).

Subjects who have already randomized to the active control group (febuxostat) on Day 1 (Visit 4) before stopping enrollment of the active control group will stay in the study and continue receiving the treatment regimen (one capsule from each of 2 bottles of LC350189 placebo and 1 bottle of febuxostat 40 mg or 80 mg) that they are initially assigned to. The subjects will receive febuxostat 40 mg on Day 1 (Visit 4) and continue to be on febuxostat 40 mg for the rest of the treatment period if their sUA is < 6.0 mg/dL on Day 14 (Visit 5). If their sUA is \geq 6.0 mg/dL on Day 14 (Visit 5), they will receive febuxostat 80 mg QD on Day 28 (Visit 6) and will continue to be on this dose for the rest of the treatment period.

Subjects randomized to the test (LC350189 50 mg, LC350189 100 mg, or LC350189 200 mg) or placebo groups before implementation of the Protocol version 5.0 will stay in the study and continue receiving 3 bottles of investigator products (2 bottles of LC350189 25mg/100mg/placebo and 1 bottle of febuxostat placebo) as they are initially assigned to.

The rest of study procedures will apply as described in Section 6.2 and the SoA ([Table 2-1](#)).

Figure 6-1 Study Design Schematic

6.2 Study Description

Visit 1: Screening visit

Before screening takes place, potential study subjects will be provided with written and oral information about the study and the procedures involved. Subjects must sign the informed consent form (ICF) prior to entering the study (further details are provided in Section 9.1.1). The screening visit to identify eligible subjects for the study will be performed 33 to 26 days prior to first dosing. All assessments performed at the screening visit are stated in the schedule of assessments (SOA) (Table 2-1) and will be recorded in the electronic case report from (eCRF) (further details are provided in Section 9.1.2). Subjects will be assigned screening numbers in an ascending order upon signing the ICF.

Visit 2: Wash-out/prophylaxis period

Following screening, enrolled subjects receiving ULT will discontinue their ULT and enter a wash-out period between Visit 2 and the start of the treatment period. All enrolled subjects will start gout flare prophylaxis with colchicine 0.6 mg (QD) 30 to 23 days prior to the first day of the treatment period to be continued throughout the treatment period. ULT wash-out and prophylaxis treatment should occur approximately 3 days after screening, once screening laboratory results are received and the subject is determined to be eligible. Subjects will record the incidence of gout flares using eDiary throughout the wash-out and prophylactic period, starting at Visit 2.

Visit 3: Assess eligibility for randomization

Subjects will attend the clinic at Day -9 to -4 to assess their eligibility for randomization. sUA will be determined based on a blood sample obtained at Visit 3 to ensure that the inclusion criterion of $sUA \geq 8.0 \text{ mg/dL}$ to $\leq 12.0 \text{ mg/dL}$ is met. Subjects with $sUA < 8$ or $> 12 \text{ mg/dL}$ at Day -9 to -4 will be excluded from further participation in the study.

Visits 4 to 8: Treatment period

All scheduled visit should occur in the morning, if possible.

On the study Day 1, eligible subjects will visit to the clinic after a fast for at least 8 hours (preferably, overnight fast) for pre-dose laboratory sample collection (Visit 4). Subjects will be randomly assigned in a 1:1:1:1 ratio to one of the following treatment groups: LC350189 50 mg, LC350189 100 mg, LC350189 200 mg, or placebo. Subjects will be randomized within the following population strata: sUA, defined as the Day -9 to -4 (Visit 3) value, $< 9.8 \text{ mg/dL}$ or $\geq 9.8 \text{ mg/dL}$, and presence or absence of tophi, as assessed by palpation, at screening (Visit 1). Note that for all subsequent evaluations of sUA, the baseline value will be the Day 1 (Visit 4) pre-dose value. Subjects will be treated with their first dose of investigational product by oral self-administration with water. Investigational product will be taken from the bottle handed out at the visit. Blood sampling for PK/PD analysis will be performed at the time points stated in the PK/PD sampling schedule (Section 9.1.14, Table 9-3). All attempts should be made to collect the blood samples at, or within 30 minutes prior to administration of investigational products for pre-dose samples and ± 10 minutes for post-dose samples of, the scheduled time. The actual time of each sampling will be

recorded on the eCRFs, as well as time that subjects take the medication ($t=0$). Additional assessments will be made per the SOA ([Table 2-1](#)).

Subjects will be instructed to fast for at least 8 hours (preferably, overnight fast) prior to returning to the clinic on Day 14 (Visit 5), 28 (Visit 6), 56 (Visit 7), and 84 (Visit 8). On Day 14, 28, 56, and 84, subjects will withhold the investigational product until pre-dose laboratory samples have been obtained. Subjects will then take investigational product on site on Day 14 (Visit 5), 28 (Visit 6), and 56 (Visit 7), and blood samples will be obtained at the time points stated in the PK/PD sampling schedule (Section [9.1.14](#), [Table 9-3](#)). The last dose of investigational product that a subject will take is on Day 83. AEs will be recorded and measurements of laboratory parameters, vital signs, and 12-lead electrocardiogram (ECG) will be performed for safety evaluation according to the SOA ([Table 2-1](#)). Subjects will record the incidence of gout flares and rescue treatment using eDiary. Subjects will be assessed for the presence of tophi by palpation at the end of treatment visit (Visit 8). All tophi will be counted and recorded on the Tophi eCRF page.

Visit 9: Follow-up

A Follow-up on site-visit will be performed on Day 98 for safety assessments ([Table 2-1](#)).

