9.1.20 Study contingency measures during the COVID-19 pandemic

Following contingency measures can be implemented to ensure safety of study participants and to manage study conduct during disruption of the study as a result of COVID-19 control measures. Site staffs should consult with the Sponsor or a Sponsor designated third party to implement

contingency measure and document the reason including but not limited to missing data or out of window visits.

Following approach can be implemented; however, further modification of existing processes may be in place depending on local situation.

Investigator should take all precautions to protect the rights, safety, and well-being of subjects.

Screening visit & Wash-out/prophylaxis period

- If subjects screen fail because subjects are unable or not willing to make visit to the site due to COVID-19, reason for screening fail should be documented as COVID-19. Rescreening will be allowed for subjects who are not able to complete screening process or randomization due to the COVID-19 pandemic related reason.
- For subjects who have passed screening at Visit 1 but are not able to make on-site visit for Visit 2, one bottle of colchicine and an eDiary device can be provided to subject alternatively by secured delivery method.

Treatment period

- Out of window visit is allowed as long as the subjects continue to take investigational products.
- If scheduled visits are significantly impacted, investigational products and colchicine for Visit 6 and 7 can be delivered direct to subjects in secure method.
- Missing visits may be allowed in case of a complete shutdown of a study site or subjects/sites' concerns with COVID-19. If a subject is unable to have labs drawn per protocol schedule, site should consult the medical monitor and/or Sponsor to review the subject's participation in the study to ensure safety of subjects for continuing in the study.
- In case of a complete shutdown of a study site per a government order or a subject being concerned with visiting the site, a home health nurse may visit a subject to assist laboratory tests and to check subject's health status.
- Site using a local laboratory would be allowed in case of shutdown of a central laboratory or vendor for sample shipment. Local laboratory is for safety assessment only.
- If a patient is diagnosed with COVID-19, an AE or SAE should be recorded and site should contact the medical monitor and sponsor to discuss.

Safety follow-up

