**Table 1: Treatment Groups**

| Group | Treatment          |
|-------|--------------------|
| 1     | Placebo            |
| 2     | LC350189 50 mg QD  |
| 3     | LC350189 100 mg QD |
| 4     | LC350189 200 mg QD |

Each subject will undergo a screening visit 33 to 26 days prior to the first day of the treatment period, which include five visits on Day 1, 14, 28, 56, and 84 (Visits 4 to 8). During the treatment period, subjects will orally self-administer LC350189 or placebo for 83 days starting on Day 1, and have a follow-up on-site visit approximately 2 weeks after the completion of the dosing period. The duration of the study will be up to 19 weeks for each subject.

Gout flare prophylaxis will consist of colchicine 0.6 mg once daily (QD) starting at Visit 2 (between Day -30 to Day -23) through the end of the treatment period.

Upon implementation of the Protocol version 5.0, enrollment to the active control group (febuxostat) will be stopped.

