#### 3.2. Study Endpoints

##### 3.2.1. Primary Endpoint(s)

The primary endpoint of this study is:

- Proportion of subjects who achieve sUA level <5.0 mg/dL at Day 84 (Visit 8)

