##### **4.4.4. Per-Protocol Analysis Set**

The Per-Protocol Analysis Set (PPS) is defined as all subjects in the FAS that are compliant with treatment and have appropriate exposure to study medication for the 12-week treatment period and without any major protocol deviations that may impact primary efficacy analysis.

Major protocol deviations that may impact the primary efficacy analysis, rules for handling subjects who ever took unassigned dose or type of study treatment, algorithm for calculating overall study treatment compliance, and cutoff treatment compliance values for PPS exclusion will be determined during a blinded data review meeting (DRM) prior to DBL. If a subject withdrew from the study prematurely without Week 12 data to assess the primary and/or key secondary endpoints, he or she may be excluded from the PPS. If a subject completed the treatment period and had sUA result within 84 days +/- 5 days, he or she will be included in the PPS.

For subjects who ever received unassigned dose of study treatment but stayed in the same dose for the entire study treatment, the subject can be included in the PPS if subject received one of the pre-defined dose in the study (LC350189 50 mg, 100 mg, 200 mg, or placebo).

The PPS will be used for supportive analyses of the efficacy endpoints, based on treatment that subjects received.

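### The documents disagree on whether dosing ends on Day 83 or runs to the day before the actual Visit 8; read literally, a Day 85 or 86 visit samples the primary urate value about 48 or 72 hours after the last dose

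*Protocol*

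**What the plan says.** Two places fix the end of dosing by study day. Protocol 6.2 states: "The last dose of investigational product that a subject will take is on Day 83." SAP 3.1 (text under Table 1) matches it: "subjects will orally self-administer LC350189 or placebo for 83 days starting on Day 1".

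Other places let the visit move, or assume that dosing runs up to it:

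- Protocol Table 2-1 and SAP 14.1 give Visit 8 a window of Day 84 ± 2, so Days 82 to 86.
- Protocol 6.1 has subjects "withhold the investigational product until after pre-dose laboratory sampling on the days of scheduled visits (Days 14, 28, 56, and 84"), and Table 9-3 lists the Day 84 draw as a pre-dose sample. SAP 10.1.2 defines the steady-state trough as the end of a dosing interval, which is 24 hours for once-daily dosing.
- Protocol 9.1.20 (COVID-19 measures): "Out of window visit is allowed as long as the subjects continue to take investigational products."
- SAP 7.2.2 sets the last-period compliance denominator as the actual Visit 8 date minus the Visit 7 date, so it expects a dose on every day up to the day before the visit.
- SAP 4.4.4 admits completers to the per-protocol set (PPS) if they "had sUA result within 84 days +/- 5 days", with no condition on time since the last dose.

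The Visit 8 sample supplies the primary endpoint (sUA below 5.0 mg/dL), the below-6.0 endpoint and the Day 84 trough concentration. The SAP gives no analysis window for the Full Analysis Set (FAS).

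**The concern.** The last dose is tied to a study day and the primary sample to a movable visit, and no sentence links them. A subject who obeys every written rule can attend inside the window and still be sampled after one or two dose-free days beyond the intended 24 hours. The SAP would analyse that value as an ordinary Day 84 result.

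Placebo subjects have no drug to wash out, so any effect falls on the active arms and lowers their observed response. Within those arms it matters most for subjects whose on-drug urate is just under the threshold. The primary objective is to find the therapeutic dose, and SAP 4.1 justifies the group size by dose selection, so the observed rate in each dose group matters as well as the test against placebo. The Day 84 trough concentration has the same problem.

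**Working it through.** **1. The plan's own figures (Protocol 12.4).** Sample size: (1.96 + 0.84)² × (0.80 × 0.20 + 0.47 × 0.53) / 0.33² = 29.45, rounded up to 30. With 20% dropout, 30 / 0.8 = 37.5, rounded up to 38. Power for 0.80 against 0.10 with 30 per group at one-sided 0.025 is 0.9999995. All agree with the protocol, and none depends on how the dosing rule is read.

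**2. Days since last dose.** If the last dose is on Day 83, the gap is the visit day minus 83. If dosing runs to the day before the actual visit, the gap is 1 day at every visit date.

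**3. Drug remaining.** Protocol 4.3 gives multiple-dose half-lives of 8.6 to 13.8 hours. Assuming first-order decline, the amount relative to the 24-hour trough after d days is 2^(−24(d − 1)/half-life).

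| Visit 8 | Days since Day 83 dose | Permitted by | Drug relative to 24-hour trough |
|---|---|---|---|
| Day 84 | 1 | protocol window | 100% |
| Day 85 | 2 | protocol window | 14 to 30% |
| Day 86 | 3 | protocol window | 2 to 9% |
| Day 89 | 6 | PPS rule only | below 0.3% |

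Days 87 and 88 (4 and 5 days) also arise only under the PPS rule.

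**4. The compliance formula exposes the contradiction.** Take Visit 7 on Day 56 and a stop on Day 83, which is 28 dosing days in the last period. With Visit 8 on Day 86, compliance is 28 / 30 = 93.3% for the period and 83 / 85 = 97.6% overall. On Day 89 it is 28 / 33 = 84.8% and 83 / 88 = 94.3%. The SAP thus counts the protocol's own stop as missed doses. A cutoff at the 80% mentioned in Protocol 8.4.1 would not remove these subjects.

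**5. Effect on sUA (illustration only).** The documents report how fast urate falls, not how fast it returns. Assume baseline 9.0 mg/dL and a return to baseline with a half-time of 24 to 72 hours, starting 24 hours after the last dose: sUA = 9.0 − (9.0 − trough) × 2^(−24(d − 1)/half-time).

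- Trough 4.5: 5.4 to 6.8 at 2 days and 6.2 to 7.9 at 3 days, so a responder at the 5.0 threshold is read as a failure.
- Trough 3.6 with a 72-hour half-time: 4.7 at 2 days, still a responder, and 5.6 at 3 days.

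**6. Effect on power.** The share of late visits is also not given. Observed response = 0.80 × (1 − share late × share of those responders lost), against placebo 0.10 with 30 per group.

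| Share late | Share of those lost | Observed response | Power |
|---|---|---|---|
| 25% | 50% | 0.70 | 99.98% |
| 50% | 50% | 0.60 | 99.3% |
| 40% | 100% | 0.48 | 92.1% |
| 50% | 100% | 0.40 | 78.0% |

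The last two rows are extreme cases, included to show where power starts to fall.

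**7. Existing safeguards.** The only sensitivity analysis (SAP 8.2) carries the last observation forward for dropouts. It leaves completers' values untouched, so it cannot reveal late sampling.

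**The case against.** The strongest reply is that Day 83 is nominal. Protocol 6.2 uses nominal days throughout, although each visit has a window, and on that pattern Day 83 means the day before Visit 8. The compliance denominator, the pre-dose label and the COVID-19 rule fit this reading. So does supply: 35 capsules per bottle from Day 56 last through Day 90. Unused drug is collected at Visit 8, so a subject seen on Day 82 could not take a Day 83 dose. This is a fair reading and may be what was meant. But no section says so, and sites could apply the text differently.

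A reader might infer that a within-window visit can come up to six days after the last dose. It cannot: the protocol window ends at three days. Four to six days arise only under the PPS rule, which is supportive. For late visits under the COVID-19 measures, Protocol 9.1.20 requires continued dosing, and other out-of-window visits need a sponsor decision (Table 2-1, footnote 2).

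Some safeguards exist. SAP 10.1.1 lists time deviations for concentration samples, SAP 4.4.5 requires evaluable data, and a blinded review settles major deviations. These may catch some trough samples. They do not touch the FAS analysis, and the ± 5 day inclusion in SAP 4.4.4 says nothing about time since dose. The Day 14, 28 and 56 results also inform dose selection and are unaffected by the last-dose rule.

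**Conclusion.** The contradiction stands and should be resolved. On the literal text, a visit inside the protocol window can take the primary sample about 48 or 72 hours after the last dose, with 14 to 30% or 2 to 9% of the 24-hour trough remaining. Those percentages assume only first-order decline at the half-lives in Protocol 4.3. The direction is downward for active-arm response, with placebo hardly affected.

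The size of the effect on response cannot be stated. A reader might conclude that most late-sampled responders would be lost, that the lower doses would suffer most, or that the primary endpoint is shown to be biased. The documents support none of these: they give no urate offset rate, no distribution of on-drug urate by dose and no late-visit share, and a deeper trough can survive one missed day in the illustration. Nor is the comparison with placebo in real doubt. At the planned rate of 0.80, power stays above 99% with up to a quarter of responders lost. What is exposed is the Day 84 response rate in each dose group, which informs dose selection, and the Day 84 trough concentration.

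**What to change.** Reconcile Protocol 6.2, Table 2-1 and 9.1.20 with SAP 3.1, 4.4.4 and 7.2.2, so that the last-dose rule, the Visit 8 window and the compliance denominator agree. Which dosing rule applies is for the sponsor to state; this review does not choose one.

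In the SAP, before database lock:

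- Derive for every completer, in all arms alike, the time from last dose to the Visit 8 sUA sample.
- Make the ± 5 day PPS inclusion also conditional on a pre-specified maximum interval since last dose.
- Add a sensitivity analysis of the primary endpoint that leaves out completers sampled beyond that interval.
- Apply the same limit to the Day 84 trough concentration.

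The cost is a clarifying sentence, one derived variable and one extra analysis. A few completers would leave the PPS. The last-dose date must also be derived for completers: SAP 7.2.2 uses it in the compliance formulas only for early terminators, so its availability for the others should be checked first.
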